9.6 Data Analyses

We will perform descriptive statistics on the sample demographics similar to our prior paper [61] including age, gender, race, ethnicity, body mass index (BMI), smoking status, and current medication use for GERD symptoms. We will also assess whether perceived stress, perceived empathy (both patient and provider), or personality type (five factor inventory) modify improvement in GERD symptoms using generalized linear models. We will use the GERD-HRQL, NIH PROMIS GERD, and GSRS as adjunct/corroborating measures of GERD symptom severity. We will also assess whether subject gender or race modifies our results. For all of these analyses, there is a risk that we will be underpowered for detecting significant effects. Qualitative interviews will be audio recorded, transcribed, and coded using standard qualitative methodologies and a grounded theory-based approach [82]. Blood samples will be processed and stored at -80°C for later omics-based analyses that will be the subject of a future grant/study.

As [name] has moved and now has a faculty appointment at the University of California, Davis (UC Davis), some data analysis will occur there under her supervision at that location. [name] and her team at UC Davis will continue to collaborate with her mentor, [name] who serves as the site PI at MGH, on this project.

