3. STUDY DESIGN

Study design: Single-center, single-blind, pilot randomized controlled trial

Primary outcomes:

- 1) Correlation between physiologic synchrony in patient-provider dyads (GSR or HRV) and improvement in GERD symptom severity.
- 2) Correlation between absolute changes in GSR within subjects over the course of the study visit and subsequent changes in GERD symptom severity.
- 3) Correlation between absolute changes in high frequency HRV within subjects over the course of the study visit and subsequent changes in GERD symptom severity.

Secondary outcomes:

- 1) The difference in the frequency of supportive provider behaviors between the standard and expanded visit groups.
- 2) The difference in the ratings of rapport, engagement, and reciprocity between the standard and expanded visit groups.

Study population:

Men and women age 21-70 with heartburn symptoms 3 or more days per week. We will enroll until we reach 24 completing subjects.

Study location:

The Clinical Research Center (CRC) at Massachusetts General Hospital (MGH), the Benson-Henry Institute (BHI) for Mind Body Medicine, or another MGH location.

Length of subject participation: 2 weeks

Length of study enrollment: 12-14 months

Groups:

- 1) Standard visit (n=8), modeled after an empathic, high quality conventional primary care visit.
- 2) Expanded visit (n=16), modeled after a visit with an integrative medicine provider

Randomization:

The randomization code will be generated by the study statistician as described below (section 4.3). The study will be single-blinded (study providers and the research team will know what the subject is receiving but the subject will not). Randomization will be

Tool Revision History

Version: 11.0

Version Date: 5.8.2020

stratified based on study provider. We anticipate 4 providers each seeing 6 subjects (2 standard visits, 4 expanded visits).

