5.4 Adherence Assessment

Subject adherence is defined by subjects completing at least 12 out of 14 days of their daily symptom diary during the two week study period. Adherence will be assessed when subjects return their symptom diaries at their follow-up visit. For subjects who return incomplete symptom diaries, average daily symptom severity for the days completed will be calculated. If there is insufficient data to make this calculation, we will assume that symptoms are unchanged from baseline.

Tool Revision History

Version: 11.0

Version Date: 5.8.2020

6. STUDY PROCEDURE**6.1 Schedule of Evaluations for Subjects/Patients**

Assessment	Telephone Screening: (Day -30 to -7)	Baseline, Enrollment, Randomization: Visit 1 (Day 0)	Post Intervention: Visit 1 (Day 0)	Follow-up: Visit 2 (Day 13-18)
Prescreen Form	X	X		
GERD Daily Symptom Diary Reviewed		X		X
Informed Consent Form		X		
Current Medication List		X		X
Height and weight		X		
Blood draw		X	X	X
Demographics & Health Behaviors		X		
GERD-Health Related Quality of Life Questionnaire (GERD-HRQL)		X		X
NIH Patient Reported Outcomes Measurement Information System (PROMIS) GERD		X		X
Gastrointestinal Symptom Rating Scale (GSRS)		X		X
Perceived Stress Scale-10 (PSS-10)		X		X
Current Stress Question		X	X	X
NEO Five Factor Inventory (NEO-FFI)		X		
Randomization		X		
HRV, respiratory rate, skin temperature, and GSR		X		
Video recording		X		
Study visit		X		
Consultation And Relational Empathy questionnaire (CARE)			X	
HEAL Patient-Provider Connection			X	
Adverse Events				X
Qualitative Interview				X
Debriefing				X

Tool Revision History

Version: 11.0

Version Date: 5.8.2020

Schedule of Evaluations for Providers

Assessment	Enrollment	Prior to each subject/patient encounter
Informed Consent Form	X	
Interpersonal Reactivity Index (IRI)	X	
NEO-FFI	X	
Demographics	X	
Intervention Training	X	
PSS-10		X
Current Stress Question		X
Fatigue Scale		X
Interview at completion of study		

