- GERD-HRQL - a validated 11 item scale for assessing the impact of GERD symptoms on health-related quality of life [70].
- NIH PROMIS GERD scale – a validated 13 item instrument assessing frequency and severity of GERD symptoms over a 7 day recall period [26].
- GSRS: The Gastrointestinal Symptom Rating Scale is a validated 15 item instrument for measuring the severity of gastrointestinal symptoms [71]. It contains 5 subscales: abdominal pain, reflux syndrome, diarrhea syndrome, indigestion syndrome, and constipation syndrome.
- Current Stress Question – 1 item self-report measure of current stress level on a scale of 0 (no stress) to 10 (extreme stress).
- Perceived Stress Scale (PSS) – a widely used 10 item measure of perceived stress that has been shown to correlate with a variety of different health outcomes [72]. We have adapted the originally validated measure to ask about stress over the past week (7 days), rather than the past month, to better fit the timeframe of the study. We have used this timeframe in other studies.
- NEO Five Factor Inventory (NEO-FFI) – a validated 60-item instrument that measures five major dimensions of personality: extraversion, neuroticism, agreeableness, conscientiousness, and openness to experience [73]. Some dimensions have been associated with response to enhanced patient-provider interactions in others studies [74].
- Physiologic Measures and Video Recording: During the intervention we will measure HRV, respiratory rate, skin temperature, and GSR in both study patients and study providers. The study visit will also be video recorded.

Evaluations for Study providers:

- Interpersonal Reactivity Index (IRI) — a validated 28 item self-assessment of cognitive and affective components of empathy [75].
- NEO Five Factor Inventory (NEO-FFI) – a validated 60-item instrument that measures five major dimensions of personality: extraversion, neuroticism, agreeableness, conscientiousness, and openness to experience [73]. Some dimensions have been associated with response to enhanced patient-provider interactions in others studies [74].
- Demographics and practice– will assess things such as age, gender, race/ethnicity, and clinical experience (see Appendix D)
- Current Stress Question – 1 item self-report measure of current stress level on a scale of 0 (no stress) to 10 (extreme stress). Study providers will complete this question immediately prior to each study subject visit.

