- Perceived Stress Scale (PSS) – a widely used 10 item measure of perceived stress that has been shown to correlate with a variety of different health outcomes [72]. Study providers will complete this questionnaire immediately prior to each study subject visit.

Tool Revision History

Version: 11.0

Version Date: 5.8.2020

- Fatigue Scale – 1 item self-report measure of the current fatigue level on a scale of 0 (no fatigue) to 10 (extreme fatigue). Study providers will complete this question immediately prior to each study subject visit.

Randomization

Subjects will be randomized on the day of their baseline visit (Visit 1), following consent, to receive either the standard or expanded visit with the particular provided that they are scheduled to see that day. We will stratify randomization by provider so that each provider does the same proportion of standard and expanded visits. Randomization will occur after subjects have completed their optional first blood draw and baseline questionnaires, immediately prior to the study visit. Study providers will open an envelope instructing them which study visit intervention to deliver.

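### Provider empathy takes about four values across 24 subjects; tested as a main effect in the section 9.6 models with no provider-level error, its standard error is too small whenever providers differ in mean symptom change

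*Combined protocol and SAP*

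**What the plan says.** - **Analysis.** Section 9.6 states: "We will also assess whether perceived stress, perceived empathy (both patient and provider), or personality type (five factor inventory) modify improvement in GERD symptoms", and gives generalized linear models as the method. It lists no model terms, provider effect, cluster-robust variance or provider-level degrees of freedom. Its only caveat is that these analyses may lack power.
- **Measure.** Section 6.2.2 describes the IRI as "a validated 28 item self-assessment of cognitive and affective components of empathy". It is the only empathy instrument that providers complete.
- **Timing.** The provider schedule in section 6.1 marks the IRI and the provider NEO-FFI at enrollment only. The PSS-10, current stress and fatigue items are repeated before each encounter; of the current stress and fatigue items section 6.2.2 says "Study providers will complete this question immediately prior to each study subject visit".
- **Number of providers.** Section 3: "We anticipate 4 providers each seeing 6 subjects (2 standard visits, 4 expanded visits"). Section 4.3 allows for only three providers, who would then share the remaining slots.
- **Contrast.** Section 9.5.2 specifies generalized linear mixed models for the video-coded outcomes, with terms for time-point, visit group and their interaction. Section 9.6 does not carry mixed models over to the empathy analysis.

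**The concern.** A trait scored once per provider is shared by all of that provider's subjects. If providers also differ in mean symptom change for any other reason, the six subjects of one provider are not six independent pieces of evidence about the trait. A model with 24 subjects as units credits them as if they were. Stratifying randomization by provider does not help: it balances visit type within provider but adds no providers.

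The consequence is a false positive, in which a chance difference among four clinicians is reported as an association between provider empathy and symptom response. The low-power caveat in 9.6 points the other way, toward missed effects. Section 9.2 says that the pilot is meant to identify features for later studies, so a spurious provider signal would have some cost, although the stated criterion for further work is the physiologic correlation.

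**Working it through.** **Plan's own figures.** The documents give none for the provider-empathy analysis. The section 9.2 figures for the primary correlation (n = 24) reproduce:
- P(r > 0.20 | ρ = 0.36) = Φ[(atanh 0.36 − atanh 0.20)·√21] = 78.8%; 80.0% by simulation; 80% stated.
- Power at ρ = 0.54, two-sided 5% = Φ[atanh 0.54·√21 − 1.96] = 79.1%; 80.9% by simulation; 80% stated.

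They do not bear on the provider analysis.

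**Inputs.** k = 4 providers, m = 6 subjects each, 4 expanded and 2 standard (sections 3, 4.3, 9.2); fallback 3 providers, about 8 subjects each. Two-sided 5% is stated in 9.2 for the primary correlation and is assumed here for 9.6. The provider ICC in symptom change is not in the documents, so a range including 0 is shown.

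**Main effect.** For a covariate constant within provider, the design effect is 1 + (m − 1)·ICC, and the true standard error exceeds the ordinary one by its square root. At ICC 0.10: 1 + 5 × 0.10 = 1.5, √1.5 = 1.22, effective N = 24/1.5 = 16. Type I error is from 40,000 simulated trials per row, with visit type and the provider score in the model and no true effect.

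| Assumed ICC | SE ratio | Effective N | Type I error, 4 × 6 | Type I error, 3 × 8 |
|---|---|---|---|---|
| 0 | 1.00 | 24 | 5.0% | 4.9% |
| 0.05 | 1.12 | 19.2 | 7.8% | 9.4% |
| 0.10 | 1.22 | 16.0 | 11.2% | 13.8% |
| 0.20 | 1.41 | 12.0 | 17.4% | 22.8% |

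(SE ratio and effective N are for 4 × 6.) A second simulation with the provider score alone (22 df) gives 8.0%, 11.3% and 17.7% at ICC 0.05, 0.10 and 0.20.

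**Test on provider means.** This keeps about 5% throughout, but with 4 − 2 = 2 df. The critical |r| is t/√(t² + df): 4.303/√(18.51 + 2) = 0.95, against 2.074/√(4.30 + 22) = 0.40 for 24 independent subjects. With three providers (1 df) it is 0.997.

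**Interaction with visit type.** A provider's overall level cancels when that provider's expanded and standard visits are compared. With no variation in visit effect between providers, the plain model rejects 4.9%, 4.7%, 4.4% and 3.8% at ICC 0, 0.05, 0.10 and 0.20. If the visit effect varies by provider, with variance 0.2 relative to a variance of 1 among standard-visit subjects (assumed), the rates are 6.9%, 6.6%, 6.3% and 6.1%. A test on the four within-provider differences (2 df) stays at about 5%.

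**Estimability.** Four provider indicators reproduce any provider-level score exactly, so a main effect of the IRI cannot be fitted beside them. The interaction can: four indicators, visit type and IRI-by-visit-type make six columns of rank six, because every provider delivers both visit types.

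**The case against.** The strongest reply concerns what 9.6 means by *modify*. The table in section 9.5 puts empathy and the patient-provider connection in the context of the visit intervention, which suggests an interaction with visit type. On that reading the inflation of the main-effect test disappears. This stands, and it limits the point. But 9.6 itself speaks of modifying symptom improvement, which is as easily read as a main effect, and the plan does not settle it.

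Other parts of the reply also stand:
- **The IRI is inferred.** Neither 9.6 nor the 9.5 table names it. The empathy rows in the table are CARE and HEAL, which patients complete and which vary by subject; this point does not apply to them in the same way.
- **Independent units are inferred too**, from the absence of any provider term in 9.6 and the contrast with 9.5.2.
- **Provider variance may be small.** Scripts, provider training, the instruction to be equally empathic and the video review (section 5.1) all aim to limit it.

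A reader might go further and infer that provider personality is caught by the same problem. The documents do not schedule such a test: the 9.5 table lists the FFI at Visit 1, the subjects' time point, and in 9.6 the mention of both patient and provider attaches to empathy only. A reader might also infer that no model with provider effects can address provider empathy. That is true of the main effect only.

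**Conclusion.** The point holds in conditional form. If the provider IRI is tested as a main effect over 24 subjects as independent units, type I error is about 5% at provider ICC 0 and about 8%, 11% and 17 to 18% at assumed ICCs of 0.05, 0.10 and 0.20; it is higher with three providers. If the intended test is an interaction with visit type, the plain model is about right or slightly conservative (about 4 to 5%), rising to about 6 to 7% under an assumed visit-effect variance of 0.2. On either reading only about four providers inform the answer.

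It would be tempting to say that the error bars are too small without qualification. The documents do not support that, because it needs between-provider variance that they do not quantify. Nor do they support saying that the next study depends on this analysis: provider empathy is neither a primary nor a secondary outcome, and the section 9.2 criterion (observed r above 0.20) concerns the physiologic correlation. The primary correlation figures are not affected.

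**What to change.** Amend section 9.6 as follows:
1. Name the provider empathy measure (the IRI, if that is meant) and say whether *modify* means a main effect or an interaction with visit type.
2. For a main effect, take the provider IRI out of the 24-subject models. Plot each provider's mean symptom change against the IRI score and describe it, or test on provider means with 2 df, noting that |r| must exceed 0.95.
3. For an interaction with visit type, fit it with provider fixed effects and state that only four providers inform it. Fixed effects remove differences in provider level but not provider variation in the visit effect; a test on the four within-provider differences allows for that variation.
4. Apply the same rule to the provider NEO-FFI only if it is used.

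Measures that vary between a provider's subjects or visits (CARE, HEAL, patient PSS-10 and NEO-FFI, pre-visit provider stress and fatigue) can stay in the 24-subject models. They may still cluster by provider, so 9.6 should say how provider enters those models.

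The cost is SAP wording, with no new data. The downside is that no useful p-value is available for the provider empathy main effect.

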10. DATA COLLECTION AND QUALITY ASSURANCE

10.1 Data Collection Forms

Blood samples will be collected at the MGH CRC. Questionnaire data will be collected on iPads at the MGH CRC or Benson-Henry Institute using Research Electronic Data Capture (REDCap; <http://project-redcap.org/>) forms, with the exception of GERD

Tool Revision History

Version: 11.0

Version Date: 5.8.2020

symptom dairies which subjects will complete either online (REDCap) or in paper format daily. Paper data will be doubled entered into a REDCap database by study personal and checked for consistency. REDCap is a secure, web-based application developed by Vanderbilt University for electronic collection and management of clinical research study data. In collaboration with Harvard Catalyst, Partners Research Computing locally hosts REDCap.

Study staff will maintain an electronic screening file and enrollment log file and paper files of consent forms.

Study participant confidentiality will be maintained by a unique identifier. An electronic file linking participants' personally identifying information and study ID will be password protected. All paper data will be stored in a locked filing cabinet. Only study affiliated personal will have access to the study database and associated files. Electronic communication with collaborators will only involve deidentified information. All published data will be presented in aggregate format and deidentified.

10.2 Data Management

All paper symptom diaries will be reviewed in real time with subjects to ensure that data can be transferred completely and accurately to electronic form. Such data will be double entered and cross checked as described above. All data (questionnaire, physiologic, video) will be cleaned by study staff and reviewed every 1-2 months by the study PI to ensure accuracy, completeness, and timeliness of subsequent analyses. All biological samples will be labeled with PIDs, logged, tracked, and stored in a securely locked specimen freezer at the BHI.

10.3 Quality Assurance

10.3.1 Training

The study PI will personally train and supervise all research coordinators and interns working on the study in collaboration with relevant consultants to ensure that study measures are collected appropriately. All research coordinators/interns will have completed the appropriate human subjects and Partners' research training programs and may complete additional training depending upon the capacity in which they will serve in the study.

10.3.2 Protocol Deviations

Protocol deviations will be documented and reported using Partners' Insight/Institutional Review Board (IRB) service as an Other Event. Unapproved major protocol deviations will be reported to the IRB and NCCIH within 5 business days of discovery.

Unapproved minor protocol deviations will be reported to the IRB at the time of the annual continuing review and to NCCIH annually as well. Should a protocol deviation become repetitive and/or problematic, the investigational team may consider submitting a protocol amendment to adjust study procedures.

10.3.3 Monitoring

The study PI will regularly review study questionnaires, HRV and GSR data, video recordings, and logs for completeness and quality. Such review will follow each subject initially but will occur at least every 1-2 months for the duration of the study.

11. PARTICIPANT RIGHTS AND CONFIDENTIALITY

11.1 Institutional Review Board (IRB) Review

This protocol and the informed consent documents and any subsequent modifications will be reviewed and approved by the Partner's IRB.

11.2 Informed Consent Forms

Written informed consent will be obtained by a study team physician at the initial study visit after reviewing inclusion and exclusion criteria, the participant's symptom diary, and the electronic medical record if the participant is a patient at a Partner's affiliated hospital. The consent form will describe the purpose of the study, the procedures to be followed, and the risks and benefits of participation. Participants will have the opportunity to ask questions. A copy will be given to each participant and this fact will be documented in the participant's record. Participants who cannot consent for themselves or who are not fluent in English will not be eligible to participate due to the nature of the study.

11.3 Participant Confidentiality

Study visits will be conducted in a private setting. Whenever possible, questionnaire data will be collected electronically using REDCap. REDCap is a secure, web-based application developed by Vanderbilt University for electronic collection and management of clinical research study data. In collaboration with Harvard Catalyst, Partners Research Computing locally hosts REDCap. All electronic data not gathered using REDCap (symptoms diaries, physiologic data, video recordings) will be stored on a Partners Research Computing shared drive which is backed up nightly to protect against data loss and is behind the Partner's firewall. Any data that cannot be collected directly onto a shared drive (i.e., must be saved on a local hard disk during data collection) will be collected on an encrypted laptop, transferred to a Partner's-affiliated server shortly after collection, and then removed from the laptop. Any paper questionnaire data will be stored in a locked filing cabinet at BHI.

Only those researchers involved in the study will have access to electronic and paper data. The file linking participants' personally identifiable information with their participant identification number (PID) will be password protected and access will be restricted to the fewest number of staff required but will include at least the PI and a research coordinator. Electronic access to videos will also be password protected. All paper records will be kept in a locked file cabinet. All computer entry and analysis will be done using PIDs only. Any data, forms, reports, video recordings, and other records that leave the site will be identified only by a PID to maintain confidentiality. Digital video files may be stored for up to 12 years but may be destroyed sooner.

For analysis of video-recorded data, we will be collaborating with [name] at Northeastern University. Video file names will be coded with participant ID numbers. We may share video data with [name] and her team using an application supported by Partners Research Computing that is similar to Dropbox but HIPAA compliant. The only personally identifiable information that will be available will be subjects' images in the

Tool Revision History

Version: 11.0

Version Date: 5.8.2020

videos. All individuals who will be accessing this data will be added to the protocol and educated in the importance of subject privacy and confidentiality.

Information will not be released without written permission of the participant, except as necessary for monitoring by IRB, the NCCIH, and the OHRP.

